#### **8.3.6.1 Hypersensitivity reaction monitoring and management**

If a study participant experiences a hypersensitivity reaction (such as rash, angioedema, or anaphylaxis), he or she will contact the clinical site immediately (24 hours a day) or seek urgent medical advice in accordance with instructions from the Investigator.

The advice will be based on the clinical presentation and may be to present to the clinical site or seek medical attention in the community.

The study participant should be rapidly and thoroughly assessed in line with the actions below.

Hypersensitivity reactions will be AESIs and require expedited reporting to UCB, regardless of seriousness, expectedness, or relatedness in line with Section 8.3.6. This will allow for rapid evaluation.

In case of a suspected hypersensitivity reaction or any clinical indication of an unexpected immune response, the points described in Sections 8.3.6.1.1 through Section 8.3.6.1.6 should be observed.

Consideration for restarting study medication is provided in Section 7.1.4.

Procedures for the management of UCB0599 are provided in Appendix 3 (Section 10.3).

##### **8.3.6.1.1 Medical history**

Detailed history of the hypersensitivity reaction (eg, rash, angioedema, or anaphylaxis) with onset time of symptoms and signs, location of symptoms and signs, first appearance, its

evolution (eg, where the rash appeared and to where it spread), any other symptoms (eg, pruritus, swelling, breathlessness), especially if showing a systemic involvement (anaphylaxis), will be recorded. The criteria for anaphylaxis are described in Section 8.3.6.1.1.1.

The clinical progression of the hypersensitivity reactions symptoms should be recorded and any change in symptoms or severity should also be recorded together with the timing.

All AEs reported concurrently should be included within the review.

It will also be important to investigate any recent intake of new medications, herbs, supplements, or the recent use of any topical substances.

### **8.3.6.1.1.1 Anaphylaxis**

Sampson et al. listed criteria for the diagnosis of anaphylaxis. This was developed at the Second National Institute of Allergy and Infectious Disease/Food Allergy and Anaphylaxis Network symposium (Sampson et al, 2006).

Acute onset=minutes to a few hours.

Criteria for diagnosis-1 or more of the following:

- Acute onset of an illness with symptom complex 1 (see below)
- Acute onset of symptom complex 2 (see below) after exposure to a likely allergen
- Acute onset of a reduced SBP after exposure to a known allergen for the participant

Symptom complex 1: both of the following:

- At least 1 of the following:
  - Skin involvement (generalized hives, pruritis, flushing)
  - Mucous membrane involvement (swollen lips, swollen tongue, swollen uvula)
- At least 1 of the following:
  - Respiratory compromise (dyspnea, wheezing, bronchospasm, stridor, reduced peak expiratory flow, hypoxemia)
  - Reduced SBP, collapse, syncope, incontinence or other symptom of end-organ dysfunction

Symptom complex 2: Two or more of the following:

- Skin or mucous membranes (as above)
- Respiratory compromise (as above)
- Reduced BP (as above)
- Persistent GI tract symptoms (cramping, abdominal pain, vomiting)

Reduced SBP is indicated by 1 of the following:

- BP <70% of Baseline SBP

## Limitations:

Treudler et al. found that the criteria may not perform as well as others for the recognition of severe, immediate reactions (Treudler et al, 2008).

### **8.3.6.1.2 Complete physical examination**

Evaluation of a possible hypersensitivity reaction includes a complete physical examination of the entire body as soon as feasible after reporting by the study participant. The complete physical examination includes a detailed description of the signs such as rash or angioedema, the location of the signs, and an examination for other possible signs, such as:

- Blanched or flushed skin
- Mucous membrane erosions or ulceration
- Maculae
- Papulae
- Blisters
- Confluent erythema
- Angioedema: face, lips, and/or tongue swelling, also back of hands or feet
- Wheeze, stridor, dyspnea
- Palpable purpura
- Lymphadenopathy

An examination of the entire skin surface, not just local to the site of reaction, is required.

Furthermore, a complete physical examination will also include:

- Vital signs (high fever, dyspnea, or hypotension)
  - Vital signs (pulse rate, SBP, diastolic BP, respiratory rate, body temperature, and oxygen saturation) will be taken when the AE of hypersensitivity is reported and at regular intervals (approximately 20 to 30 minutes) for a minimum of 2 hours. The frequency thereafter will be based on clinical judgement. If there is worsening of clinical status, the Investigator will apply the appropriate treatment and safety procedures (eg, call emergency) and contact the UCB study physician.
- Photography of rash and other symptoms at the first opportunity and with reasonable time sequence to document resolution. If timely site visit is not possible the participant may be requested to take photos to ensure photos of active symptoms. If participant is requested to provide photos the Investigator should advise the participant in data protection requirements (eg, avoidance of identifying features such as characteristic tattoos, parts of the face). The Investigator will ensure that identifiable characteristics are removed/hidden before sharing the pictures with the Sponsor.
- Re-examination should the symptoms significantly worsen
- Occurrence of other recent or current symptoms, even if they appear not related

### **8.3.6.1.3 Additional investigations**

Investigators should arrange for the following investigations; further investigations may be requested after consultation with the Medical Monitor:

- Additional blood sampling for extended etiological characterization of the hypersensitivity reaction including:
  - Basophil Activation Test
  - Lymphocyte Transformation Test assays
  - Tryptase
  - Immunoglobulin E
- Rapid referral to experts (ie, dermatologist, allergist, or immunologist)

Additionally, a skin biopsy may be considered following review by expert.

### **8.3.6.1.4 Treatment**

Investigators will administer the appropriate treatment as deemed necessary in cases of hypersensitivity. This includes the use of antihistamines for urticaria and the appropriate management in case of potentially life-threatening events such as anaphylaxis, Stevens-Johnson Syndrome, and toxic epidermal necrolysis.

### **8.3.6.1.5 Blood sampling**

Blood samples should be taken as soon as possible for safety and/or for further identification of the underlying mechanism of the reaction (hematology: eosinophilia; chemistry: check renal function including electrolytes, liver function tests, immunology, and IgE). Specific laboratory parameters (eg, cytokines, tryptase, complement, high-sensitivity C-reactive protein) will be collected at Day -1, and will be stored and used only in case of a hypersensitivity event (see Section 1.3).

The timing of the blood collection and other details for each test will be specified in the laboratory manual, and the full set of clinical laboratory tests are provided in Appendix 2 (Section 10.2).

### **8.3.6.1.6 Rapid referral to experts**

Expert consulting (eg, dermatologist/allergist/immunologist) is required for expert opinion (diagnosis), diagnostic testing (eg, prick test for other potential allergens), further treatment, and follow up. Same day referral is required, especially if there is presentation of systemic symptoms and/or signs.

### **8.3.6.2 Renal function safety monitoring and management**

If a participant develops clinically significant renal dysfunction, repeat laboratory testing should be undertaken as soon as possible and other appropriate investigations may be arranged. An increase in serum creatinine of >25% from the previous value will trigger repeat testing within 48 hours. The Medical Monitor should be notified, and consideration should be given to more frequent monitoring.

Clinically significant renal dysfunction will trigger an SMC review.

Participants must be discontinued from study medication (but not necessarily from the study) if laboratory tests suggest evidence of renal toxicity (see Section 7.1.3 for renal toxicity stopping criteria and Section 7.2 for participant discontinuation/withdrawal from the study). Any clinically significant findings in laboratory results for renal function will be monitored until resolution or stabilization.

The SMC charter will include further details regarding the assessment of renal function.

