**Table 3-2: Part B: The safety, tolerability, and PK of UCB0599 after administration of UCB0599 at single dose in healthy participants of Japanese and Chinese origins**

Objectives	Endpoints
Primary	

 
To assess the safety and tolerability of UCB0599 after administration of a single dose of an oral formulation in healthy participants of Japanese and Chinese origins
 
To evaluate the plasma PK of UCB0599 after administration of a single dose of an oral formulation in healthy participants of Japanese and Chinese origins
 
	
Safety endpoint
 
 
Incidence of TEAEs
 
Incidence of treatment-emergent SAEs
 
Incidence of TEAEs leading to withdrawal from study
 
 
Co-primary PK endpoints for UCB0599
 
 
<math>C_{max}</math>
 
<math>AUC_{0-t}</math>
 
<math>AUC_{inf}</math>
 

Other	

 
To assess additional safety and tolerability characteristics of UCB0599 in healthy participants of Japanese and Chinese origins
 
	
Other safety endpoints
 
 
Changes from Baseline in vital signs (pulse rate, blood pressure [BP], respiratory rate, and body temperature)
 

**Table 3-2: Part B: The safety, tolerability, and PK of UCB0599 after administration of UCB0599 at single dose in healthy participants of Japanese and Chinese origins**

Objectives	Endpoints

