### 7.1.3 Renal toxicity stopping criteria

Participants must be discontinued from the study medication if renal toxicity considered possibly related to the study treatment occurs.

Laboratory tests suggestive of renal toxicity which should trigger further assessment may include:

- Increase in serum creatinine  $\geq 0.3\text{mg/dL}$  from Baseline **OR**
- Increase in serum creatinine to  $\geq 1.5$  times from Baseline **OR**
- New persistent albuminuria or clinically significant increase in preexisting albuminuria.

Any clinically significant findings in laboratory results for renal function will be monitored until resolution or stabilization.

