## **7.2 Participant discontinuation/withdrawal from the study**

Participants are free to withdraw from the study at any time, without prejudice to their continued care.

A participant may withdraw from the study at any time at his/her own request, or may be withdrawn at any time at the discretion of the Investigator for safety, behavioral, compliance, or administrative reasons.

If the participant withdraws consent for disclosure of future information, the Sponsor may retain and continue to use any data collected before such a withdrawal of consent.

If a participant withdraws from the study, he/she may request destruction of any samples taken and not tested, and the Investigator must document this in the site study records.

See the Schedule of Activities (Section 1.3) for data to be collected at the time of study discontinuation and follow up and for any further evaluations that need to be completed.

Participants should be withdrawn from the study if any of the following events occur:

1. Participant develops a clinically relevant medical condition (physical or psychiatric) that, in the opinion of the Investigator, jeopardizes or compromises the study participant's ability to participate in the study or makes it unsafe to continue.
2. Participant is noncompliant with the study procedures or medications in the opinion of the Investigator.

3. Participant's laboratory tests suggest evidence of renal toxicity.
4. Participant takes prohibited concomitant medications as defined in this protocol.
5. Participant withdraws his/her consent.
6. There is confirmation of a pregnancy during the study, as evidenced by a positive serum pregnancy test.
7. Participant has an anaphylactic reaction after their first administration.
8. The Sponsor or a regulatory agency requests withdrawal of the participant.

Investigators should attempt to obtain information on study participants in the case of withdrawal.

Investigators should contact the UCB Medical Monitor, whenever possible, to discuss the withdrawal of a study participant in advance. See Appendix 1 (Section 10.1 for details on study discontinuation).

Participants who withdraw in Part A will not be replaced, and participants who withdraw in Part B will be replaced up to a maximum of 6 study participants.

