## 10.6 Appendix 6: Liver safety – suggested actions and follow up assessments

Participants with PDILI must be assessed to determine if study medication must be discontinued. In addition, all concomitant medications and herbal supplements that are not medically necessary should also be discontinued.

Investigators should attempt to obtain information on participants in the case of study medication discontinuation to complete the final evaluation.

Participants with PDILI should not be withdrawn from the study until investigation and monitoring are complete. All results of these evaluations and observations, as well as the reason(s) for study medication discontinuation and/or participant withdrawal (if applicable), must be recorded in the source documents. The eCRF must document the primary reason for discontinuation of study medication.

A specific monitoring plan must be agreed between the UCB study physician and the Investigator for participants who have ALT >5 ULN. The monitoring plan should include any necessary follow up assessments (until resolution of the abnormal laboratory values).

Phase 1 liver chemistry stopping criteria are designed to assure participant safety and to evaluate liver event etiology (see Section 7.1.1 and Table 10-1).

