5.1.1.2 Protocol Deviations

Protocol deviations are specified in Appendix 1 (Section 6.1.2).

All protocol deviations will be reviewed at the Data Cleaning Meetings (DCM) and decisions made on whether they should be considered important or not.

Important protocol deviations (IPDs) are deviations from the protocol which could potentially have a meaningful impact on study conduct or on either the primary or key secondary outcome(s) for an individual study participant. The criteria for identifying such protocol deviations will be defined within the IPD specifications document.

Important protocol deviations will be categorized as follows:

2. Inclusion/exclusion criteria deviations
3. Incorrect treatment or dose administered
4. Procedural non-compliance
5. Prohibited concomitant medication use
6. Withdrawal criteria deviation

All IPDs will be reviewed as part of the ongoing data cleaning process and data evaluation. At least one Data Evaluation Meeting (DEM) will be performed prior to the final database lock after all data have been verified/coded/entered into the database to discuss exclusion of study participants from analysis populations.

Participants may be excluded from the safety set if they do not pass the inclusion/exclusion criteria. However, should a participant be mistakenly dosed despite failing the inclusion/exclusion criteria, then their safety data would need to be reported as part of the safety analysis. Participants may be excluded from other analysis sets, but this will be determined on a case-by-case basis. If the deviation is deemed to have the potential to bias the analyses for the duration of the study then the whole participant may be removed in a sensitivity analysis on the key endpoints. The removal of the participant and the rationale will be clearly documented within the relevant TFLs.

Important protocol deviations will be identified and classified by the deviation types in the IPD document. A listing of all IPDs identified at the DCMs will be presented for all participants based on the safety set and will include the deviation type and description.

The IPDs will be tabulated using the SS, separately for Part A and Part B and will present the deviation type and description by treatment group.

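### Protocol 7.2 item 3 and Protocol 8.3.6.2 give different study status for the same renal laboratory finding

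*Protocol*

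**What the plan says.** Three protocol sections deal with a possible renal toxicity.

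- **Section 7.2** opens its list with "Participants should be withdrawn from the study if any of the following events occur". Item 3 of the list is that the participant's "laboratory tests suggest evidence of renal toxicity".
- **Section 8.3.6.2** states: "Participants must be discontinued from study medication (but not necessarily from the study) if laboratory tests suggest evidence of renal toxicity". It then refers the reader to 7.1.3 for the stopping criteria and to 7.2 for discontinuation and withdrawal.
- **Section 7.1.3** states: "Participants must be discontinued from the study medication if renal toxicity considered possibly related to the study treatment occurs". Its creatinine and albuminuria findings come under a different lead-in: "Laboratory tests suggestive of renal toxicity which should trigger further assessment may include".

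For liver injury, Protocol 10.6 settles study status explicitly: "Participants with PDILI should not be withdrawn from the study until investigation and monitoring are complete".

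Study withdrawal feeds an endpoint. Protocol Section 3 lists "Incidence of TEAEs leading to withdrawal from study" as a primary safety endpoint in Part B and a secondary one in Part A. SAP 5.2 also tabulates, by treatment sequence, the participants who leave the study because of an adverse event.

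**The concern.** Sections 7.2 and 8.3.6.2 use the same trigger words and reach different results on study participation. Under 7.2 the participant should leave the study. Under 8.3.6.2 the drug must stop and the participant may stay. Two participants with the same laboratory result could be classified differently depending on which section the investigator opened. What is at stake is whether a renal event is counted as a study withdrawal, and whether the participant goes to an early termination visit or keeps the remaining visit schedule.

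**Working it through.** The plan states no figure on this point, so the check is a comparison of texts followed by a trace through the SAP outputs.

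**1. The rules side by side**

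| Place | Trigger | Study medication | Study participation |
|---|---|---|---|
| Protocol 7.2, item 3 | "laboratory tests suggest evidence of renal toxicity" | Not addressed separately | Should end |
| Protocol 8.3.6.2 | The same words | Must stop | Need not end |
| Protocol 7.1.3 | Toxicity judged possibly related; suggestive tests listed separately | Must stop for possibly related toxicity; suggestive tests lead to assessment | Not addressed |
| Protocol 10.6 (liver) | Potential drug-induced liver injury | Assess whether to stop | Continues until the work-up is complete |

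Rows 1 and 2 differ only in the last column. Section 7.1.3 does not say that the drug stops *only* for related toxicity, so it is softer than 8.3.6.2 without contradicting it.

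**2. Does the dosing outcome differ?** In-treatment laboratory tests are scheduled on Days 14 and 33 in Part A and Days 5 and 10 in Part B (Protocol Tables 1-3 and 1-4). Doses still to come are:

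- Part A Day 14: 3 (Days 19, 24 and 29)
- Part A Day 33: 0
- Part B Day 5: 1 (Day 6)
- Part B Day 10: 0

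Withdrawal under 7.2 and the mandatory stop under 8.3.6.2 both cancel those doses. Only study status differs.

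**3. Can such an event be a TEAE?** SAP 5.5.2 extends the TEAE window to 4 days after the last treatment. Day 33 − Day 29 = 4 and Day 10 − Day 6 = 4. Days 14 and 5 fall between doses. All four tests lie inside the window.

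**4. Which outputs change?**

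- *Study discontinuation because of an adverse event (SAP 5.2, by sequence).* The event counts if 7.2 is followed and need not count if 8.3.6.2 is followed. One participant is 1/7 = 14.3 points of a planned Part A sequence. In a Part B active sequence it is 1/4 = 25 points within one origin, or 1/8 = 12.5 points if the origins are pooled. These figures give the weight of a single event. They are not an expected effect.
- *The withdrawal endpoint.* The SAP 5.5.2 list of adverse event summaries has TEAEs that led to discontinuation and does not say whether of drug or of study. If it means drug, a renal TEAE that stops dosing counts under either rule. If it means study, the event counts under 7.2 and need not count under 8.3.6.2. An effect is possible but not established.
- *Completers (SAP 5.2).* A participant who either stops dosing or withdraws before the follow-up visit is a non-completer. After Day 5 or Day 14 the two rules give the same answer. After Day 10 or Day 33 no dose is left to stop, so withdrawal alone decides and the answer can differ.

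**5. Does follow-up differ?** Sections 7.1.3 and 8.3.6.2 both require monitoring of significant renal findings until they resolve or stabilize, with no condition on study status. A participant who leaves early still has the safety follow-up procedures at the early termination visit.

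**The case against.** The strongest reply is that the texts can be made to work together. Section 8.3.6.2 says what must happen to the drug, while 7.2 only says what should happen to participation. The protocol does not treat every 7.2 event as automatic withdrawal: Protocol 10.4 lets a pregnant participant either stop medication or be withdrawn, although 8.3.5 repeats the withdrawal wording. Section 7.2 asks for prior contact with the Medical Monitor where possible, and there is only one site. Section 8.3.6.2 also assigns roles, with 7.1.3 for stopping and 7.2 for withdrawal.

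Part of this stands. There is no strict contradiction, because withdrawing every such participant would satisfy both sections. But the parenthesis in 8.3.6.2 would then do nothing. The pointer to 7.2 does not help either, because it leads back to item 3. The same 7.2 lead-in covers withdrawn consent, which is not a matter of advice.

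A reader might infer four stronger points. The documents do not support them.

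- *A participant could be re-dosed in Part B on Day 6 after an abnormal Day 5 result.* This requires reading 7.1.3 alone. Section 8.3.6.2 bars the dose, and Protocol 6.7 gives further grounds to stop.
- *A retained participant would be an important deviation.* SAP 5.1.1.2 has a category "Withdrawal criteria deviation", but the criteria are left to a separate specification that is not among the documents. A category label does not show how such a case would be classed.
- *The endpoint moves by 12.5 points in a Part B dose-by-origin cell (1/8) or 2.4 points for a Part A formulation (1/42).* These figures assume a summary of TEAEs that led to study withdrawal, by dose or formulation. SAP 5.5.2 does not define one clearly.
- *Renal follow-up is lost.* It continues under either rule.

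**Conclusion.** The inconsistency is real, lies in current text, and is minor. One laboratory trigger leads to study withdrawal in 7.2 and to a drug stop with participation allowed in 8.3.6.2. The SAP does not resolve this. The clear consequence is for the by-sequence table of study discontinuation because of an adverse event. The withdrawal endpoint may also be affected, depending on how the SAP 5.5.2 discontinuation summary is read. Dosing and renal monitoring are not affected. The documents give no renal event rate, so the size cannot be stated.

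This rests on the protocol and SAP alone. The SMC charter is to hold more on renal assessment and has not been seen. It could guide the site in practice, but the two protocol sections would still disagree.

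**What to change.** Let 8.3.6.2 govern. Either delete item 3 from 7.2, or reword it as discontinuation of study medication under 8.3.6.2, with the participant kept in the study for scheduled safety assessments and for renal monitoring until the finding resolves or stabilizes. That is in line with the liver rule in 10.6. Nothing protective is lost, because 7.2 still lets the investigator withdraw a participant for safety, and its item 1 still covers a condition that makes it unsafe to continue.

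The cost is one text edit in 7.2. Sample size, visit schedule, dosing and planned analyses do not change.

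The assessment triggers in 7.1.3 should stay as they are. Making them automatic stops whatever the relatedness would let a creatinine rise of 0.3 mg/dL end dosing. After Part A Day 14 that would cost all three elevated-pH doses, with no replacement and no rechallenge route, since 7.1.6 covers Part B only. That is a clinical trade-off, and correcting the mismatch does not require it.
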